At baseline, laboratory tests, collection of first morning void urine and 24h urine will be performed. To minimize the number of subjects likely to undergo spontaneous disease remission from entering the study and potentially biasing the results through over-representation in any of the study arms, those subjects in whom the 24h urine protein level or anti-PLA2R antibody titer fall by more than 50% compared to first measurement at screening or run-in visit, and those in whom the 24h urine protein level has fallen below 3.5g/24h will be considered a baseline failure and will not proceed to receive any study drug. Baseline period can be extended in case of delays in receiving the anti-PLA2R results.

Subjects are randomized on Day 1 or up to 4 days before, only after eligibility is confirmed, to LNP023 or rituximab.

Treatment period (subjects randomized to the LNP023 treatment arm)

Treatment period lasts for 24 weeks from Day 1 to Day 169:
Commercially Confidential Information

Treatment period (subjects randomized to the rituximab treatment arm)

- Day 1 and Day 15: a dose of rituximab 1 g by intravenous infusion (i.v.), will be administered (refer to [Section 6.1.1](#) for more details).
- Subjects should receive pre-medication consisting of an anti-pyretic and an antihistamine (e.g. paracetamol and diphenhydramine) before each dose as per local standards. Where a single dose of glucocorticoid (e.g. methylprednisolone or hydrocortisone) is used in addition to these measures as part of local standard of care, then this is permitted.
- Treatment period will continue till Day 169 without any further rituximab administration.

Safety follow-up and EOS

A safety follow-up period of 29 weeks will follow the treatment period. A call should be performed 30 days after the last day of the treatment period (Day 199, week 28), and a study visit will be performed on Day 266 (Week 37). Subjects may be treated according to local standard of care throughout this follow-up period. All treatments administered should be documented in the study Case Report Forms.

An EOS visit is scheduled on Day 378 (week 53).

Please refer to [Section 8](#) for details regarding assessments to be performed.

4 Rationale

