4.5.3 Potential safety risks for rituximab

The known adverse events and potential safety risks for rituximab (the reference treatment) include: infusion reactions, the large majority of which occur in association with the first infusion and within 24 hours of infusion, severe mucocutaneous reactions, hepatitis B reactivation, sometimes resulting in fulminant hepatitis, hepatic failure and death, and progressive multifocal leukoencephalopathy resulting in death. For detailed information on these risks and other AEs, refer to the SmPC/local country label. It is recommended that rituximab infusion is discontinued for severe reactions and that medical treatment is provided for Grade 3 and Grade 4 infusion-related reactions. Rituximab should be discontinued in the event of severe mucocutaneous reactions, hepatitis B virus reactivation or progressive multifocal leukoencephalopathy.

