6.6.2 Recommended treatment of adverse events

At present, there is insufficient information to provide specific recommendations regarding treatment of AEs for LNP023 arm. There is no treatment that can reverse the activity of LNP023. LNP023 is a small molecule CCI. Potential AEs should therefore be treated symptomatically at the discretion of the investigator. Medication used to treat AEs must be recorded on the concomitant medications/significant non-drug therapies CRF.

Rituximab-related AEs should be treated in accordance with local guidelines. Patients who develop infusion reactions should be monitored closely. The rituximab infusion should be discontinued and medical treatment with corticosteroids, antihistamine and paracetamol should be administered in accordance with local guidelines for severe reactions. Rituximab therapy should be discontinued in the event of severe mucocutaneous reactions, hepatitis B reactivation, neurological complications or other serious adverse events deemed by the investigator to be treatment related.

Where response to treatment is deemed inadequate the investigator may, at their discretion, withdraw the subject from the study and commence local standard of care. Subjects should continue with the scheduled study visits to allow collection of outcome and adverse event data.

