12.5.2 Safety endpoints

For all safety analyses, the safety set will be used. All tables will be presented by treatment group.

Safety summaries (tables, figures) include only data from the on-treatment period with the exception of baseline data which will also be summarized where appropriate (e.g. change from baseline summaries). In particular, summary tables for adverse events (AEs) will summarize only on-treatment events, with a start date during the on-treatment period (treatment-emergent AEs).

The on-treatment period in the LNP023 treatment groups lasts from the date of first administration of study treatment to 30 days after the date of the last actual administration of any study treatment. The on-treatment period in the rituximab treatment group lasts from the first administration to 6 months after the date of the second administration. Subjects who received a single rituximab infusion are considered under treatment until 3 months after this single infusion.

Adverse events

All information obtained on adverse events will be displayed by treatment group and subject.

The number (and percentage) of subjects with treatment emergent adverse events (events started after the first dose of study medication or events present prior to start of treatment but increased in severity based on preferred term) will be summarized in the following ways:

- by treatment, primary system organ class and preferred term;
- by treatment, primary system organ class, preferred term and maximum severity;
- by treatment, Standardized MedDRA Query (SMQ) and preferred term.

Separate summaries will be provided for study medication related adverse events, death, serious adverse events, other significant adverse events leading to discontinuation.

The number (and proportion) of subjects with adverse events of special related to identified and potential risks (i.e. systemic bacterial infection, anaemia, abnormalities of thyroid function and testicular symptoms and / or abnormalities of reproductive hormone levels) will be summarized by treatment.

A subject with multiple adverse events within a primary system organ class is only counted once towards the total of the primary system organ class.

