## **7 Statistical methods for safety and tolerability data**

For all safety analyses, the safety analysis set will be used. All tables will be presented by treatment group. Baseline is defined as the last non-missing measurement prior to randomization.

Safety summaries (tables, figures) will include only data from the on-treatment period with the exception of baseline data which will also be summarized where appropriate (e.g. change from baseline summaries).

The on-treatment period in the LNP023 treatment groups lasts from the date of first administration of study treatment to 30 days after the date of the last actual administration of any study treatment. The on-treatment period in the rituximab treatment group lasts from the first administration to 6 months after the date of the second administration. Subjects who received a single rituximab infusion are considered under treatment until 3 months after this single infusion.

Summary statistics of continuous data will include n, mean, SD, median, minimum and maximum, while categorical data will be summarized as frequencies and percentages.

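### In both arms the on-treatment safety window runs about 26 to 30 days into follow-up, when new immunosuppression is allowed, and no visible rule separates adverse events that start after it

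*Protocol*

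**What the plan says.** **LNP023 window.** Protocol 12.5.2 defines the on-treatment period as running from the date of "first administration of study treatment to 30 days after the date of the last actual administration of any study treatment". SAP 7 repeats the rule: the period ends "30 days after the date of the last actual administration of any study treatment".

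**Rituximab window.** The same two sections run it to six months after the second infusion, or three months after a single infusion.

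**Entry to the tables.** Under protocol 12.5.2, AE summary tables take events whose start date lies in the on-treatment period. Nothing visible there or in SAP 7 makes this depend on other therapy.

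**End of treatment and follow-up.** For LNP023, protocol section 3 states: "Treatment period lasts for 24 weeks from Day 1 to Day 169". The rituximab treatment period also continues to Day 169. Under Safety follow-up and EOS the same section says: "Subjects may be treated according to local standard of care throughout this follow-up period". It gives no washout, and it requires all follow-up treatments to be documented in the CRF.

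**Prohibited medication.** In protocol Tables 6-2 and 6-3, the bans on immunosuppressants and biologics cover the time up to the end of the randomized treatment period. The live-vaccine rows of both tables foresee immunosuppression starting during safety follow-up.

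**Inadequate response.** Protocol 6.6.2 lets the investigator "withdraw the subject from the study and commence local standard of care", with scheduled visits and AE collection continuing.

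**Infusion reactions.** Protocol 4.5.3 lists these among the known rituximab risks, "the large majority of which occur in association with the first infusion and within 24 hours of infusion".

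**The concern.** Safety and tolerability of LNP023 is the first secondary objective, and the by-arm tables of treatment-emergent AEs, serious AEs and AEs of special interest serve it. If a subject starts another immunosuppressant in early follow-up and reacts to it, the event falls inside the window and is shown under the study drug. That can happen in either arm.

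New therapy soon after Day 169 is plausible. The population is nephrotic and selected for high risk of progression (protocol sections 3 and 4.1), no study drug is supplied after the study (9.2), and rituximab is described as widely used in this disease (8.3.1).

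The event types matter. Systemic bacterial infection is named as an AE of special interest in protocol 12.5.2 and in SAP 7.2, and it could also follow a new immunosuppressant. An infusion reaction under LNP023, an oral capsule, would be a plain misattribution in an all-cause table.

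**Working it through.** **1. LNP023 window, completers.** Inputs: treatment ends on Day 169 (protocol section 3); the window closes 30 days after the last dose (12.5.2, SAP 7).

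- 169 + 30 = Day 199. This reproduces the protocol's own Day 199 for the 30-day safety call.
- Follow-up days inside the window: 199 − 169 = 30 (Days 170 to 199). With the last capsule on Day 168 the window closes on Day 198, leaving 29.
- Share of the window: 30/199 = 15.1%.

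**2. Rituximab window, both infusions given.** Inputs: second infusion on Day 15; six months taken as 180 to 184 days (my assumption, since the documents give no day count).

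- 15 + 180 = Day 195; 15 + 184 = Day 199.
- Follow-up days inside the window: 195 − 169 = 26, to 199 − 169 = 30.
- After a single infusion on Day 1, three months (90 to 92 days) closes the window at Day 91 to 93, so there is no overlap.

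The overlap is therefore almost the same in the two arms: about 30 days against 26 to 30.

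**3. Are those days open to new therapy?** Section 3 allows standard of care throughout follow-up. The bans in Tables 6-2 and 6-3 end with the treatment period, and both tables anticipate immunosuppression in follow-up. No sentence names rituximab as follow-up therapy; that it may be used is inferred from the lapsed ban, the open permission and the stated wide use.

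**4. What differs between arms.** A rituximab-arm subject has the first infusion on Day 1, as study drug, and it is correctly counted under rituximab. An LNP023 subject switched to rituximab between Day 170 and Day 199 has a first infusion inside the LNP023 window. By protocol 4.5.3, most infusion reactions come with that infusion and within a day of it. For infections and other toxicity of new therapy, the documents do not settle which arm is affected more.

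**5. Size.** The documents give neither the uptake of new therapy nor the risk of an AE after it. What can be stated:

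- One subject in 24 is 1/24 = 4.2 percentage points; two are 8.3.
- Illustration only: let q be the share of 24 subjects who start new therapy in the overlap, and r the share of those with a resulting AE in it. Expected subjects = 24 × q × r. With q and r each from 10% to 50%, this is 24 × 0.01 = 0.24 to 24 × 0.25 = 6.0. The chance of at least one is 1 − 0.99^24 = 0.21 to 1 − 0.75^24 = 0.999.
- Restricting the base to likely non-remitters: protocol 4.3 cites 35.1% complete or partial remission on rituximab in a randomized trial against supportive care. If LNP023 were similar, (1 − 0.351) × 24 = 15.6 subjects would not be in remission. With q = 25% to 50% and r = 10% to 30%, 0.4 to 2.3 subjects are affected (1.6 to 9.7 points of 24).

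These ranges show only that the answer is driven by assumed inputs.

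**The case against.** **A fixed window after the last dose is a legitimate choice, and treatment-emergent tables record timing, not cause.** This stands. The window also captures delayed effects of LNP023, the study is non-confirmatory, and the safety summaries are descriptive. Causality is recorded for each AE, study-medication-related events have their own summary, concomitant medications are listed and summarized, and AEs are displayed by subject, so a careful reader could trace individual cases. The mitigation is partial. The related-AE summary rests on investigator judgment in an open-label trial, and neither it nor the listings change the all-cause counts or the registry tables built on treatment-emergent events (SAP 7.2).

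**A reader might infer that the rule works against LNP023 alone.** The documents do not support that. The rituximab window reaches almost as far into follow-up, and the permission covers both arms. Only the first-infusion asymmetry is documented.

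**A reader might also put a firm figure on the inflation, for example 3 to 15 percentage points in the LNP023 arm.** That range comes from assuming that 25% to 50% of all 24 subjects switch and 10% to 30% of those react. The upper end has 12 subjects switching within 30 days, 77% of the roughly 15.6 expected non-remitters. A subject with an earlier event in the same table row would add nothing to the count.

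**Rapid switching may be rare.** It may. Protocol 4.1 says remission takes at least six months on existing treatments and wants follow-up data on persistence of effect. After Day 169 the next contacts are the Day 199 call and the Day 266 visit.

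**For subjects who stop LNP023 early, one might read 6.6.2 as opening standard of care at once.** Table 6-2 keeps immunosuppressants and biologics prohibited until the end of the treatment period. The two provisions conflict, so this point does not rest on early stoppers.

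**Redacted text may hold a further rule.** It may; the statement concerns visible text only.

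**Conclusion.** The point holds for both arms as a gap in how the safety tables are specified. For subjects who complete treatment, the window takes in about 30 follow-up days on LNP023 and about 26 to 30 on rituximab, taking six months as 180 to 184 days. In those days new immunosuppressants or biologics are permitted, and no visible rule in protocol 12.5.2 or SAP 7 separates events that follow them.

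The planned windows are not wrong in themselves, and the documents do not establish a net bias against LNP023. The one directional element is the first rituximab infusion of a switched LNP023 subject. The number of affected subjects cannot be derived from the documents. Each one changes an incidence by up to 4.2 points in an arm of 24, provided that the subject is not already counted in that row. Related-AE summaries and medication listings reduce the risk of misreading but do not remove it. A low-cost addition to the tables is worthwhile.

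**What to change.** In protocol 12.5.2 and SAP 7:

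- Keep the planned on-treatment windows and the full-window tables.
- Derive for each subject the start date of the first non-study immunosuppressant or biologic, using the medication classes already listed in Tables 6-2 and 6-3. Non-study rituximab counts in both arms; permitted infusion pre-medication does not.
- In both arms, present treatment-emergent AEs, serious AEs and AEs of special interest in two parts: onset before that date, and onset from that date to the end of the window. Give person-time for each part.
- Base between-arm safety statements on the first part, alongside the full-window tables.

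Separately, protocol 6.6.2 and Table 6-2 (and Table 6-3 for rituximab) must be reconciled for subjects who stop treatment early or respond inadequately, so that the status of standard of care before Day 169 is clear.

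Cost: one derived date from data already recorded in the CRF, and one extra set of tables. The first part has slightly less observation time, which the person-time makes visible. Late effects of the study drug after a switch still appear in the second part and in the full-window tables.

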## **Adverse events**

All information obtained on adverse events will be displayed by treatment and subject.

The number and percentage of subjects with treatment-emergent adverse events will be summarized in the following ways:

- by treatment, primary system organ class (SOC) and preferred term (PT)
- by treatment, primary system organ class (SOC), preferred term (PT) and maximum severity
- by treatment, Standardized MedDRA Query (SMQ) and preferred term (PT).

Separate summaries will be provided for study medication related adverse events, death, serious adverse events, other significant adverse events leading to discontinuation.

The number and proportion of subjects with adverse events of special interest related to identified and potential risks (i.e. systemic bacterial infection,

Commercially Confidential Information  
will be  
summarized by treatment.

A subject with multiple adverse events within a primary system organ (SOC) class is only counted once towards the total of the primary system organ class (SOC).

Adverse events which will be counted for a specific treatment period are those which are treatment-emergent. These events are those with an onset at or after the start of the treatment period that were absent pre-treatment, or which were present prior to the start of the treatment period but increased in severity, or changed from being not suspected to being suspected of study drug relationship, or developed into SAEs after the start of the treatment period based on preferred term (PT).

Heatmaps will be provided by treatment group displaying the on- and off-set of the most severe AEs in a subject over time.

For the legal requirements of ClinicalTrials.gov and EudraCT, two required tables on treatment emergent adverse events which are not serious adverse events with an incidence greater than **5%** and on treatment emergent serious adverse events and SAE suspected to be related to study treatment will be provided by system organ class and preferred term on the safety set population.

If for a same patient, several consecutive AEs (irrespective of study treatment causality, seriousness and severity) occurred with the same SOC and PT:

- a single occurrence will be counted if there is  $\leq 1$  day gap between the end date of the preceding AE and the start date of the consecutive AE
- more than one occurrence will be counted if there is  $> 1$  day gap between the end date of the preceding AE and the start date of the consecutive AE.

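### The on-treatment adverse-event window closes at different times by arm for subjects who stop early, so crude LNP023 percentages can be modestly understated

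*Protocol*

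**What the plan says.** Protocol 12.5.2 and SAP section 7 set the same rule.

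- **Rituximab:** "The on-treatment period in the rituximab treatment group lasts from the first administration to 6 months after the date of the second administration". There is a shorter window for incomplete dosing: "Subjects who received a single rituximab infusion are considered under treatment until 3 months after this single infusion".
- **LNP023:** the window runs from first administration "to 30 days after the date of the last actual administration of any study treatment".
- **Tables:** "Safety summaries (tables, figures) will include only data from the on-treatment period", apart from baseline values.
- **Measure:** in SAP 7.2, "The number and percentage of subjects with treatment-emergent adverse events will be summarized in the following ways": by system organ class and preferred term, by maximum severity, and by standardized MedDRA query. Protocol 12.5.2 uses the same measure.

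The readable text has no exposure-adjusted rate, time-to-event summary or common-window summary of adverse events. SAP 7.2 summarizes LNP023 exposure in weeks and rituximab exposure as number of doses, both separately from the adverse events. It also provides by-subject displays of all adverse events, and heatmaps of the onset and offset of the most severe ones.

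Protocol 9.1.1 keeps subjects who stop treatment in the study and on the assessment schedule where possible. Protocol 10.1.1 continues adverse-event monitoring to the end-of-study visit where that is later than 30 days or 5 half-lives after the last dose.

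**The concern.** The LNP023 window moves with the date of the last capsule and can close early on any treatment day. Once both rituximab infusions are given, nothing that happens later shortens that subject's window. Two subjects with the same event on the same day can therefore be treated differently: the event is tabulated for the rituximab subject and left out for the LNP023 subject who had stopped more than 30 days before.

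Percentages of subjects take no account of this. A reader cannot rebuild patient time from the exposure summaries either, because weeks in one arm and infusion counts in the other are not comparable.

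Safety and tolerability of LNP023 is the first secondary objective, and Protocol 8.3.1 expects the rituximab arm to help compare safety as well as efficacy. With about 24 subjects per arm, one subject can move a term across the 5% threshold of the registry table in SAP 7.2: 1/24 = 4.2% is below it and 2/24 = 8.3% is above.

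**Working it through.** **Inputs from the documents.** LNP023 treatment Day 1 to Day 169, rituximab on Day 1 and Day 15, and follow-up call on Day 199 (Protocol section 3). Window rules (Protocol 12.5.2, SAP 7). About 24 subjects per arm and 17% drop-out (Protocol 12.8.1).

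**Window ends for subjects dosed as planned.**
- LNP023 completer: 169 + 30 = Day 199. This reproduces the protocol's own Day 199.
- Rituximab, both infusions: 15 + 181 to 184 days (six calendar months) = Day 196 to 199. With the ±2-day visit window and six months taken as 180 to 183 days: 13 + 180 = Day 193 to 17 + 183 = Day 200.
- Rituximab, one infusion: 1 + 90 to 92 days = Day 91 to 93.

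**LNP023 subjects who stop early.** Window end = stop day + 30; share = window end / 199.

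| Last dose | Window closes | Share of 199 days |
|---|---|---|
| Day 29 | Day 59 | 30% |
| Day 57 | Day 87 | 44% |
| Day 85 | Day 115 | 58% |
| Day 113 | Day 143 | 72% |
| Day 141 | Day 171 | 86% |
| Day 168 | Day 198 | 99% |

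**Effect on a crude percentage.** Assumptions that are not in the documents:
- the same constant hazard λ in both arms;
- a share d of LNP023 subjects stopping, with stop day s uniform on Days 1 to 168;
- every rituximab subject fully infused;
- d = 17%, borrowed from the trial-wide drop-out rate because no capsule-stopping rate is given.

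With risk p over a 197-day rituximab window, λ = −ln(1 − p)/197.

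Crude LNP023 % = (1 − d)·[1 − exp(−199λ)] + d·mean over s of [1 − exp(−(s + 30)λ)]

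Mean coverage: the mean stop day is 84.5, so a stopper covers 114.5/199 = 57.5%, and the arm covers 0.83 + 0.17 × 0.575 = 92.8%.

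For p = 30%: λ = 0.3567/197 = 0.00181. A completer's risk is 30.25%, a stopper's mean risk about 18.4%, and 0.83 × 30.25 + 0.17 × 18.4 = 28.2%.

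| Risk over 197 days | LNP023 %, nobody stops | LNP023 %, 17% stop | Ratio | Subjects lost of 24 |
|---|---|---|---|---|
| 10% | 10.1 | 9.4 | 0.93 | 0.17 |
| 30% | 30.3 | 28.2 | 0.93 | 0.48 |
| 50% | 50.4 | 47.3 | 0.94 | 0.74 |
| 80% | 80.3 | 76.5 | 0.95 | 0.93 |

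With d from 4% to 30% the relative loss runs from about 1% to 13%. At p = 30% the crude figure is 29.8% (d = 4%) or 26.7% (d = 30%). Only at d = 30% with common events does the loss pass one subject: 1.31 of 24 at p = 50%, 1.64 at p = 80%.

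**Offset in the rituximab arm.** A single-infusion subject is cut at about Day 92. At p = 30% that subject's counted risk is 1 − exp(−92 × 0.00181) = 15.3% instead of 30%. One such subject in 24 lowers the rituximab percentage by 14.7/24 = 0.6 points, against about 2.0 points on LNP023.

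**The case against.** A reader might infer that LNP023 rates are understated whenever subjects stop capsules, and that worse tolerability necessarily produces a more favourable table. The documents do not support this. A percentage of subjects changes only if the first event of that type starts after last dose plus 30 days and before about Day 199. A late stop loses almost nothing. The event that prompted the stop normally falls inside the window, and events leading to discontinuation have their own summary. Single-infusion rituximab subjects are also cut, so the net direction depends on how often each kind of stop occurs.

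Other points against:
- The rule is the same in both documents, so it looks deliberate. A longer window after rituximab is plausible: Protocol 5.2 requires contraception for 12 months after rituximab and 1 week after LNP023. As a summary of events on drug plus 30 days, the LNP023 table is valid.
- The 17% is a planning figure for drop-out. Subjects lost from the study supply no later events under any window, and drop-out would shorten rituximab follow-up too.
- The standard error of 30% with 24 subjects is √(0.3 × 0.7/24) = 9.4 points, far larger than the 2-point shift.
- The alternatives have faults. Protocol 4.5.3 says most infusion reactions come with the first infusion and within 24 hours, so dividing by about 197 days dilutes them. Protocol 6.6.2 allows local standard of care after an inadequate response while visits continue, so a common window could charge those events to LNP023.
- No formal between-arm test of adverse events is described, and redacted text may hold further analyses.

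These points limit the size of the concern and rule out replacing the crude tables. They do not remove the unequal time at risk. Side-by-side percentages will be read as a comparison, and the listings, heatmaps and exposure summaries do not put the arms on the same footing.

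**Conclusion.** The point holds in a limited form. The on-treatment windows agree for subjects dosed as planned and diverge for LNP023 subjects who stop early, and the readable plan shows only crude percentages over those unequal windows. The LNP023 figures can then be modestly low relative to a common window, partly offset if some rituximab subjects receive one infusion.

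Under the stated assumptions (17% stopping uniformly, constant equal hazard, full rituximab dosing), the loss is about 5-7% in relative terms and under one subject in 24. It grows with more or earlier stopping, and is zero for any term on which the stoppers had already been counted. In a non-confirmatory study this is a minor improvement to reporting. It does not show that the planned safety tables are wrong.

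**What to change.** Keep the crude on-treatment tables. Add to SAP 7.2 before database lock, as supplementary output for any adverse event, serious adverse events and adverse events of special interest, one or both of:

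1. Exposure-adjusted incidence by arm: subjects with the event per 100 patient-years, counting time from first dose to first event or the end of that subject's on-treatment window.
2. Number and percentage of subjects with an event from Day 1 to Day 199, for all treated subjects regardless of stopping.

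State the limits beside them. The rates assume a roughly constant hazard and dilute early infusion reactions. The common window includes off-drug time and possibly local standard of care. Any between-arm statement on adverse events should be read with these outputs and not rest on the crude percentages alone.

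The cost is a few columns or one extra table, with no new data collection planned. One check is needed first. Protocol 9.1.1 continues assessments only where possible, and the text for randomized subjects in Protocol 10.1.3 ends serious-event collection 30 days after treatment discontinuation or the last study visit, without saying which governs for early stoppers. The sponsor should confirm that collection through Day 199 is intended for them.
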